4.1 PRIMARY AND SECONDARY ENDPOINTS

4.1.1 Primary Efficacy and Safety Endpoints:

The co-primary endpoints for efficacy evaluations are:

1. Eyestrain caused by glare score. This will be assessed using eyestrain patient reported outcomes.
2. Monocular distance visual acuity on LogMAR scale using ETDRS charts.

The primary endpoint for safety evaluation is physiological findings (grade 3 or higher) using slit lamp. The measures include edema, corneal neovascularization, corneal staining, conjunctival injection, tarsal abnormalities, and other complications using the FDA slit lamp grading scale 0 to 4, where 0 = none, 1 = trace, 2 = Mild, 3 = moderate and 4 = severe.

4.1.2 Secondary Efficacy and Safety Endpoints:

The secondary endpoints are average daily wear time (in hours) and presence of ocular symptom (yes/no).

Both primary and secondary endpoints will be evaluated at each follow-up visit.

The subject's adverse events, keratometry changes, lens deposit, reasons for discontinuation, lens damage, number and reasons for unscheduled lens replacement, overall comfort, overall vision and overall handling will be monitored at the follow-up visits.

4.1.3 Primary Hypotheses:

1. Efficacy (Eyestrain caused by glare): Subjects wearing the JVICI Investigational Test contact lenses on a daily wear basis report eyestrain caused by glare that is, on average, significantly lower to that of subjects wearing ACUVUE® OASYS® contact lenses on a daily wear basis. The assessments will be made at the 2-, 4-, 8- and 12-week follow-up visits.
2. Efficacy (Visual Acuity): Subjects wearing the JVICI Investigational Test contact lenses on a daily wear basis report an average distance monocular logMAR visual acuity that is statistically no different to that of subjects wearing ACUVUE® OASYS® contact lenses on a daily wear basis. The assessments will be made at the 2-, 4-, 8- and 12-week follow-up visits.
3. Safety (Slit Lamp Findings): Subjects wearing the JVICI Investigational Test contact lenses on a daily wear basis have a percentage of grade 3 or higher slit lamp findings that is statistically no different to that of

subjects wearing ACUVUE® OASYS® Contact Lenses on a daily wear basis. The assessments will be made at each follow-up visit.

4.1.4 Secondary Hypotheses:

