1.4. Statistical Hypotheses for Study Objectives

This is a feasibility study and all the following hypotheses are exploratory in nature. Further analysis may be considered at the discretion of the Study Responsible Clinician.

1.4.1. Primary Hypotheses:

Efficacy

- The Test lens [REDACTED] will be significantly lower than the Control lens (ACUVUE® OASYS®), with respect to Eyestrain caused by glare score. The assessments will be made at the 2-, 4-, 8- and 12-week follow-up visits.
- The Test lens [REDACTED] will be statistically no different than the Control lens (ACUVUE® OASYS®) with respect to distance monocular LogMAR visual acuity. The assessments will be made at the 2-, 4-, 8- and 12-week follow-up visits.

Safety

- The Test lens [REDACTED] will be statistically no different than the Control lens (ACUVUE® OASYS®) with respect to percentage of eyes with grade 3 or higher slit lamp findings (Biomicroscopy). The assessments will be made at each follow-up visit.

1.4.2. Secondary Hypotheses:

Efficacy

- The Test lens [REDACTED] will be statistically no different than the Control lens (ACUVUE® OASYS®) with respect to average wearing time. The assessments will be made at the 2-, 4-, 8- and 12-week follow-up visits.

Safety

- The Test lens [REDACTED] will be statistically no different than the Control lens (ACUVUE® OASYS®) with respect to the percentage of reported symptoms, problems or complaints (yes/no). The assessments will be made at each follow-up visit.

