% = nx100/N; SD = Standard Deviation

a SLF reported during an unscheduled visit were included in the following scheduled visit.

b The percent (%) of Any SLF Grade 2 is calculated using Total Unique Eyes as a denominator.

Primary Safety Endpoint (Slit Lamp Findings):

The power was estimated from the formula given by Diggle et al. (2002)² for clustered binary data for a pre-specified sample size of N=50 per arm:

$$Z_{\beta} = \frac{\left[\sqrt{\frac{N \cdot \{n(p_1 - p_2)^2\}}{1 + (n-1) \cdot \rho}} - Z_{\alpha} \sqrt{2\bar{p}\bar{q}} \right]}{\sqrt{(p_1 q_1 + p_2 q_2)}}$$

where p_1 : Response proportion in group 1 (Test), $q_1 = 1 - p_1$, p_2 : Response proportion in group 2 (Control), $q_2 = 1 - p_2$, $\bar{p} = (p_1 + p_2)/2$, $\bar{q} = 1 - \bar{p}$, n : number of observations per cluster(n was set to 10; 2 eyes x 5 time points), N is the number of subjects per arm and ρ is the common correlation across the n observations. The term z_{α} is the z score that correspond to the pre-specified type I error error α . The term z_{β} is the z score that corresponds to the estimated power $1 - \beta$ for pre-specified size effects.

There were no SLF of grade 3 or 4 reported in any of the three studies. Using previous research in the *literature*^{4,5}, the anticipated proportion of eyes with any SLF grade 3 and 4 is estimated to be less than or equal to 0.5% in both test and control arms.

Table 2: Power calculation for various effect sizes and correlations for SLF

Test Proportion	Control Proportion	Delta	Rho	Power
0.001	0.0510	.005	0.25	33%
0.001	0.0510	.005	0.50	58%
0.001	0.0510	.005	0.75	71%
0.0025	0.0525	.005	0.25	36%
0.0025	0.0525	.005	0.50	61%
0.0025	0.0525	.005	0.75	73%
0.005	0.0550	.005	0.25	40%
0.005	0.0550	.005	0.50	64%
0.005	0.0550	.005	0.75	75%
0.01	0.0600	.005	0.25	48%
0.01	0.0600	.005	0.50	69%
0.01	0.0600	.005	0.75	78%

Primary Efficacy Endpoint (Visual Acuity):

The power calculations were performed using Diggle's formula (*Diggle et al.*; 2002)² for clustered continuous data for a pre-specified sample size of N=50 per arm:

$$Z_{\beta} = \sqrt{0.5 * \left(\frac{N(n[\frac{\mu_1 - \mu_2}{\sigma^2}]^2)}{1 + (n-1)\rho} \right)} - Z_{\alpha}$$

Where σ^2 is the assumed common variance in the two groups, $\mu_1 - \mu_2$: the difference in means between the two groups (Test - Control), n : number of observations per cluster, N is the number of subjects per arm and ρ is the common correlation across the n observations.

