The plan is to enroll 60 eligible subjects per arm with a target completion of 50 subjects per arm. During the enrollment period, the subject dropout rate will be closely monitored, if unexpectedly high dropout rate is observed in certain arm(s), the targeted total enrollment number will be increased accordingly in order to ensure a minimum of 50 subjects per group to complete the 3-month follow-up. Below is a table of power calculations for different effect sizes and correlations.

Table 3: Power calculation for various effect sizes and correlations for LogMAR Visual Acuity

Rho	Effect Size	Power
0.10	0.10	95.1%
0.25		95.4%
0.50		96.0%
0.75		96.3%
0.10	0.25	74.0%
0.25		77.2%
0.50		81.1%
0.75		84.0%
0.10	0.50	14.8%
0.25		20.1%
0.50		28.8%
0.75		36.5%

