5. EFFICACY

5.1. Analysis Specifications

5.1.1. Level of Significance

All planned analysis for this study will be conducted with a two-sided type I error rate of 5% for primary and secondary hypotheses. Adjustment for multiple comparisons across time will be performed using Bonferroni's method. Both adjusted and unadjusted results will be reported.

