5.2.2. Analysis Methods

Efficacy Analysis:

Visual Acuity

Contact lens monocular distance best-corrected visual acuity (BCVA) on LogMAR scale will be analyzed using a linear mixed model to test for the differences between the Test and Control group at each follow-up visit. Lens group, time (1-, 2-, 4-, 8- and 12-weeks) and the interaction between lens and time will be included as fixed effects in the model; and investigator site, subject and eye nested within subject as random effects when appropriate. The covariance between residuals from the same eye and subject at different time points will be selected based on the finite-sample Corrected Akaike's Information Criterion. Covariance structures considered include Compound Symmetry (CS), Heterogeneous Compound Symmetry (CSH), Spatial Power (SP(POW)), *Ante*-dependence (ANTE(1)) and unstructured (UN). For ANTE (1) and SP (POW) structures, site, subject and eye nested within subject will be included as random effects. For the remaining structures only site and subjects will be included as random effects. The covariance structure that returns the lowest Akaike Information Criteria Corrected (AICC) will be selected as the structure that best fit the data. Heterogeneous residuals covariance structures (R-side) across lens groups will be considered when appropriate. The log-likelihood ratio test will be used to test for the homogeneity between the residual covariance structures. The Kenward and Roger method will be used for the denominator degree of freedom.

Comparisons between the Test and the Control groups will be conducted at each time point using a t-test on least-square means from the repeated measure analysis. Adjustment for multiple comparisons across time will be performed using Bonferroni's method with alpha equal to 0.01(0.05/5). The corresponding simultaneous confidence intervals of least-square means differences will be calculated with 99% confidence. Unadjusted multiple comparisons will be calculated with 95% confidence for each comparison.

Average Wear Time (AWT)

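### The co-primary acuity hypothesis of no difference has no logMAR margin or reading rule, and SAP Table 3 prints 1 minus power under the heading Power

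*SAP*

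**What the plan says.** Protocol 4.1.3 expects that Test wearers will "report an average distance monocular logMAR visual acuity that is statistically no different to that of subjects wearing" the control lens. SAP 1.4.1 repeats this "with respect to distance monocular LogMAR visual acuity". Acuity is a co-primary efficacy endpoint (protocol 4.1.1), and all hypotheses are declared exploratory (protocol 3.1, SAP 1.4).

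The analysis in SAP 5.2.2 is a linear mixed model to test for differences: "Comparisons between the Test and the Control groups will be conducted at each time point using a t-test on least-square means". Alpha is 0.01 per visit (0.05/5), and "The corresponding simultaneous confidence intervals of least-square means differences will be calculated with 99% confidence", with unadjusted 95% intervals as well. On sidedness, SAP 5.1.1 says: "All planned analysis for this study will be conducted with a two-sided type I error rate of 5% for primary and secondary hypotheses". It adds "Both adjusted and unadjusted results will be reported", without saying which set governs.

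SAP 1.5 gives a power formula for clustered continuous data with N = 50 per arm. It defines n only in words ("number of observations per cluster, N is the number of subjects per arm") and gives no value of n or alpha for acuity. Table 3, "Power calculation for various effect sizes and correlations for LogMAR Visual Acuity", then lists 12 values for effect sizes 0.10, 0.25 and 0.50.

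**The concern.** A non-significant test for a difference does not show that two lenses perform alike. Showing that needs a stated difference that would matter, and an interval that excludes it. The SAP plans the interval but states no such difference for the between-arm mean, no criterion for the interval, and no rule for combining visits. The only reading the plan leaves for its co-primary hypothesis is a p-value above a threshold, and even the threshold is open, because adjusted and unadjusted results are both reported.

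Table 3 is where a reader would look to see how much weight a non-significant result can bear, and it points the wrong way. It suggests that a 0.10 SD difference is detected about 95% of the time, and a 0.50 SD difference less than 40% of the time. Power cannot fall as the effect grows.

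**Working it through.** **Reproducing Table 3.** Inputs from SAP 1.5: N = 50 per arm; eye correlation rho = 0.10, 0.25, 0.50, 0.75; effect size d, read as the mean difference divided by the SD. The formula is

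z_beta = sqrt(0.5 × N × n × d² / (1 + (n − 1) × rho)) − z_alpha, power = Phi(z_beta).

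The SAP itself says z_beta corresponds to power. Because n and alpha are not stated, I tried 36 pairs: n in {1, 2, 4, 5, 8, 10} with one-sided alpha in {0.05, 0.025, 0.0125, 0.01, 0.00625, 0.005}. No setting tried gives the table as power. As 1 minus power, n = 2 (two eyes, one visit) with z = 2.326 (one-sided 0.01) fits:

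100 × Phi(2.326 − sqrt(0.5 × 50 × 2 × d² / (1 + rho)))

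| d | Printed as power (rho 0.10 / 0.25 / 0.50 / 0.75) | 1 minus power | Power |
|---|---|---|---|
| 0.10 | 95.1 / 95.4 / 96.0 / 96.3 | 95.07 / 95.49 / 95.99 / 96.34 | 4.9 / 4.5 / 4.0 / 3.7 |
| 0.25 | 74.0 / 77.2 / 81.1 / 84.0 | 73.92 / 77.19 / 81.14 / 83.89 | 26.1 / 22.8 / 18.9 / 16.1 |
| 0.50 | 14.8 / 20.1 / 28.8 / 36.5 | 14.81 / 20.16 / 28.76 / 36.46 | 85.2 / 79.8 / 71.2 / 63.5 |

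The largest gap is 0.11 point. The next-best pair (n = 2, alpha 0.0125) misses by up to 3.2 points.

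**Power at the alpha levels the SAP plans**, same formula (%):

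| d | Two-sided 0.01 | Two-sided 0.05 |
|---|---|---|
| 0.10 | 2.9 / 2.7 / 2.4 / 2.2 | 10.3 / 9.7 / 8.9 / 8.3 |
| 0.25 | 18.7 / 16.0 / 12.9 / 10.8 | 39.2 / 35.3 / 30.3 / 26.7 |
| 0.50 | 78.7 / 72.1 / 62.2 / 53.9 | 92.1 / 88.5 / 82.3 / 76.2 |

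**How often a real difference would be non-significant.** The standard error of the mean difference is sqrt(2 × (1 + rho) / 100) SD = 0.158, 0.173, 0.187 SD for rho 0.25, 0.50, 0.75. The four-visit rows come from 400,000 simulated normal vectors per case, with an assumed between-visit correlation of 0.3 to 0.7.

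| True difference | Non-significant at | Two-sided 0.01 | Two-sided 0.05 |
|---|---|---|---|
| 0.25 SD | one visit | 84-89% | 65-73% |
| 0.50 SD | one visit | 28-46% | 11-24% |
| 0.25 SD | all four visits | 57-77% | 28-53% |
| 0.50 SD | all four visits | 3-24% | 0.4-8% |

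The available SAP text gives no logMAR SD. If it is 0.06 to 0.12 (assumption), 0.25 SD is 0.015-0.030 logMAR and 0.50 SD is 0.030-0.060.

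**Week 1.** Protocol 4.1.3, SAP 1.4.1 and SAP 5.2.1 name weeks 2, 4, 8 and 12 for acuity, and the Visit 2 steps in protocol 4.7.1 contain no ETDRS measurement. The acuity models in SAP 5.2.2 and protocol 9.1 include week 1 and divide alpha by five. Protocol 4.1.2 says every follow-up visit, and the schedule tables tick logMAR acuity in one column covering Visits 2 to 8. SAP 5.2.2 uses 0.05/4 for eyestrain and wear time. Dividing by five instead of four widens the intervals by 2.576/2.498 = 1.031, or 3.1%.

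**The case against.** The hypotheses are exploratory and the sample size was not based on a calculation, so correcting Table 3 changes no sample size, test or estimate. Enrolment may be raised to keep 50 completers per arm. Neither document says a non-significant result will be reported as similarity, intervals are already planned, and SAP 8.3 has a second statistician check that interpretations are valid. This limits the harm and is why the point ranks as a should-fix. It does not make the table right, and the second statistician has no stated criterion to check against.

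The documents do contain acuity thresholds: 0.17 logMAR for dispensing and continuance, and the one- and two-line summaries in SAP 6.4. These apply to single eyes or subjects and are not a margin for the mean difference between arms.

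The values of n and alpha behind Table 3 are inferred. The match fixes only z = 2.326, which is also two-sided 0.02, so the apparent one-sidedness is not a statement by the SAP. Either way, it differs from the planned two-sided 0.01 or 0.05. Acuity SDs may also have been lost from Table 1, whose note defines SD although only slit lamp counts appear in the available text. The logMAR conversions therefore stay illustrative.

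The schedule tick is weak evidence for week 1, because the same column covers Visits 7 and 8, which have no ETDRS step. The mismatch between SAP 5.2.1 and 5.2.2 remains.

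**Conclusion.** The concern holds. Table 3 is wrong as labelled: it reports the chance of a non-significant result. This is certain from its direction alone, since it falls with effect size and rises with rho, contrary to the formula above it; the cell-by-cell match shows how it arose. If the column was meant as the chance of finding no difference, it illustrates the first problem, because it would show success 74-84% of the time with a true 0.25 SD difference.

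The absence of a margin or reading rule is a matter of text. Its size in SD units depends on 50 per arm and the eye correlation; the four-visit figures also rest on the assumed visit correlation, and the logMAR figures on the assumed SD. The week-1 conflict is real but minor.

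**What to change.** 1. **Correct Table 3** and state n, alpha and sidedness, either as power to detect a difference or as the probability of meeting the rule in item 2. Check Table 2 (slit lamp findings) at the same time. Using n = 10, z = 2.326 and the 0.05 gap between its two proportion columns, it also reproduces as 1 minus power: 33.2 / 58.3 / 70.8 against the printed 33 / 58 / 71 in its first three rows.

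2. **Before acuity is compared by arm, choose one reading rule.**
   - (a) The sponsor states a logMAR margin and judges the planned interval against it. If the hypothesis stays as no difference, the whole interval must lie within plus or minus the margin. If only the upper limit of Test minus Control is used, reword protocol 4.1.3 and SAP 1.4.1 to not worse. State whether the claim is made per visit (adjusted interval) or needs all visits (95% intervals then suffice).
   - (b) Limit the conclusion to no difference detected, reported with the interval. This needs no margin and also serves the slit lamp, wear time and symptom hypotheses.

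3. **Reconcile week 1.** If four visits stand, drop the week-1 level and use 0.0125 with 98.75% intervals. If week 1 is meant, add it to the hypotheses and definition (SAP 1.4.1, 5.2.1) and to the Visit 2 steps.

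The cost is one or two corrected tables and a few sentences, plus a small protocol correction if the hypothesis wording or Visit 2 steps change.

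Option (a) has a price: a tight margin may not be attainable. With 50 per arm, no true difference, rho 0.25 to 0.75 and 80% power, the smallest workable margins are:

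| Rule | No difference | Not worse |
|---|---|---|
| Per visit, 98.75% interval | (2.498 + 1.282) × SE = 0.60-0.71 SD | (2.498 + 0.842) × SE = 0.53-0.63 SD |
| Per visit, 99% interval (2.576 in place of 2.498) | 0.61-0.72 SD | 0.54-0.64 SD |
| All four visits, 95% intervals (visit correlation 0.3-0.7 assumed) | 0.59-0.72 SD | 0.52-0.65 SD |

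At an assumed SD of 0.06 to 0.12, the first row is 0.036-0.085 logMAR for no difference and 0.032-0.075 for not worse.

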1	
Concomitant Medications and Medical History Review
 
Record the concomitant medications and review the subject's medical history, specifically noting any changes from baseline.
	
2	
Wearing Time
 
Record the average wearing time and comfortable wearing time.
	
3	
Compliance
 
Confirm compliance with the prescribed wear schedule, including adherence to the rub regime.
	
4	
Use of Lens Rewetting Drops
 
The subjects will record the approximate daily use of lens rewetting drops (i.e., how many times per day on average).
	
5	
Subject-reported Ocular Symptoms
 
The subject will respond to a Symptoms Questionnaire.
	

VISIT 2: 7-DAY FOLLOW-UP

(Follow-up #1, 6-8 days after Visit 1)

The following information will be collected:

Steps		Details	
6	Glare Questionnaire	The subject will respond to the Eyestrain Caused by Glare Questionnaire in regards to their study lenses.	
7	Project-Specific Questionnaire	The subject will respond to the Project-Specific Questionnaire	
8	CLUE Follow-up Questionnaire	The subject will respond to the CLUE Follow-up Questionnaire	
9	Patient Reported Outcomes	
Subjects will respond to the following individual questions.
 
 1. Subjective Comfort (Item ID: ISOC0001) 2. Subjective Vision (Item ID: ISOV0001) 3. Subjective Handling (Item ID: ISOH0001) 	
10	Lens Preferences	Subjects will respond to preference questions relating back to their habitual lenses.	
11	GSI Product Performance Questionnaire	Subjects will respond to the GSI Product Performance Questionnaire.	
12	Entrance Visual Acuity	Record the distance visual acuity with the study contact lenses (OD, OS, and OU) to the nearest letter. Smaller lines must be shown until the subject incorrectly identifies at least 50% of the letters.	
13	Spherical Over-refraction	Perform a spherical over-refraction OD and OS using any acceptable means (i.e., phoropter, trial lenses, flipper bars) in normal room illumination and record the resultant distance Snellen visual acuity OD and OS.	
14	Lens Fit Assessment:	
Subjective Assessment of the Lens Fit. If the fit is graded as unacceptable based on the criteria below, then the subject is discontinued from the study and will not be replaced.
 
 1. Limbal exposure in any gaze 2. Edge lift 3. Insufficient and/or excessive movement in all three movement categories 	

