15	Lens Deposits	Record the front and back surface deposits of the lenses.	
16	Lens Wettability	Record the white light lens wettability of both lenses.	

VISIT 2: 7-DAY FOLLOW-UP

(Follow-up #1, 6-8 days after Visit 1)

The following information will be collected:

Steps		Details	
17	Lens Damage	Lens damage (draw in source document and describe). Replace lens if damaged and complete the Product Quality Complaint form and save lens in vial with Optifree PureMoist or saline.	
18	Temporary Lens Removal & Storage	The lenses will be removed and temporarily stored in suitable lens case with Opti-Free PureMoist or saline. The lenses should not be rubbed and will be reinserted in step 21.	
19	Slit Lamp Findings	Slit Lamp Classification Scale [REDACTED] will be used to grade the findings. Record only whole numbers. Note: Subject must be free of any FDA grade 3 or greater slit lamp findings with no active ocular infection/inflammation.	
20	Eye Rinse	The study coordinator, investigator, or technician will rinse the subject's eyes thoroughly with saline.	
21	Lens Re-Insertion	The same lenses removed in step 18 will be placed back on the eyes and worn for an additional 6-8 days.	
22	Exit Visual Acuity	Record the distance Snellen visual acuity with the study lenses (OD, OS, and OU) to the nearest letter. Smaller lines must be shown until the subject incorrectly identifies at least 50% of the letters.	
23	Follow-up Visit Scheduling	An appointment for the next visit should be made for approximately 7 days (range 6-8 days) after Visit 2. Subjects should be advised to wear the study lenses at least 6 hours a day, and a minimum of 5 days per week. The study lenses must be worn into the Follow-up Visit.	

VISIT 3: 14-DAY FOLLOW-UP

(Follow-up #2, 6-8 days after Visit 2)

The following information will be collected:

Steps		Details	
1	Concomitant Medications and Medical History Review	Record the concomitant medications and review the subject's medical history, specifically noting any changes from baseline.	
2	Wearing Time	Record the average wearing time and comfortable wearing time.	
3	Compliance	Confirm compliance with the prescribed wear schedule, including adherence to the rub regime.	

VISIT 3: 14-DAY FOLLOW-UP

(Follow-up #2, 6-8 days after Visit 2)

The following information will be collected:

Steps		Details	
4	Use of Lens Rewetting Drops	The subjects will record the approximate daily use of lens rewetting drops (i.e., how many times per day on average).	

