5	Subject-reported Ocular Symptoms	The subject will respond to a Symptoms Questionnaire.	
6	Glare Questionnaire	The subject will respond to the Eyestrain Caused by Glare Questionnaire in regards to their study lenses.	
7	Project-Specific Questionnaire	The subject will respond to the Project-Specific Questionnaire	
8	CLUE Follow-up Questionnaire	The subject will respond to the CLUE Follow-up Questionnaire	
9	Patient Reported Outcomes	Subjects will respond to the following individual questions. 1. Subjective Comfort (Item ID: ISOC0001) 2. Subjective Vision (Item ID: ISOV0001) 3. Subjective Handling (Item ID: ISOH0001)	
10	GSI Product Performance Questionnaire	Subjects will respond to the GSI Product Performance Questionnaire.	
11	Entrance Visual Acuity	Record the distance visual acuity with the study contact lenses (OD, OS, and OU) to the nearest letter. Smaller lines must be shown until the subject incorrectly identifies at least 50% of the letters.	
12	Spherical Over-refraction	Perform a spherical over-refraction OD and OS using any acceptable means (i.e., phoropter, trial lenses, flipper bars) in normal room illumination and record the resultant distance Snellen visual acuity OD and OS.	
13	LogMAR (ETDRS) Visual Acuity	Using the Sekonic light meter with ISO1 setting of 125 under high illumination (>7.3 EV) and high chart luminance (9.9-10.7 EV) record the distance ETDRS high contrast: 1. OD: Chart HC1 2. OS: Chart HC2 3. OU: Chart HC3	

VISIT 3: 14-DAY FOLLOW-UP

(Follow-up #2, 6-8 days after Visit 2)

The following information will be collected:

Steps		Details	
14	Lens Fit Assessment:	
Subjective Assessment of the Lens Fit. If the fit is graded as unacceptable based on the criteria below, then the subject is discontinued from the study and will not be replaced.
 
 1. Limbal exposure in any gaze 2. Edge lift 3. Insufficient and/or excessive movement in all three movement categories 	
15	Lens Deposits	Record the front and back surface deposits of the lenses.	
16	Lens Wettability	Record the white light lens wettability of both lenses.	
17	Lens Damage	Lens damage (draw in source document and describe). Replace lens if damaged and complete the Product Quality Complaint form and save lens in vial with Optifree PureMoist or saline.	

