Contact lens monocular distance best-corrected visual acuity (BCVA) on logMAR scale will be analyzed using a linear mixed model to test for the differences between the Test and Control group at each follow-up visit. Lens group, time (1-, 2-, 4-, 8- and 12-week) and the lens group by time interaction will be included as fixed effects in the model; and investigator site, subject and eye nested within subject as random effects when appropriate.

The covariance between residuals from the same eye and subject at different time points will be selected based on the finite-sample Corrected Akaike's Information Criterion. Covariance structures considered include Compound Symmetry (CS), Heterogeneous Compound Symmetry (CSH), Spatial Power (SP(POW)), *Ante*-dependence (ANTE(1)) and unstructured (UN). For ANTE(1) and SP(POW) structures, site, subject and eye nested within subject will be included as random effects. For the remaining structures only site and subjects will be included as random effects. The covariance structure that returns the lowest Akaike Information Criteria Corrected (AICC) will be selected as the structure that best fit the data. Heterogeneous residuals covariance structures (R-side) across lens groups will be considered when appropriate. The log-likelihood ratio test will be used to test for the homogeneity between the residual covariance structures. The Kenward and Roger method will be used for the denominator degree of freedom.

Comparison between the Test and the Control groups will be conducted at each time point using a t-test on least-square means from the repeated measure analysis. Adjustment for multiple comparisons across time will be performed using Bonferroni's method with alpha equal to 0.01 (0.05/5). The corresponding simultaneous confidence intervals of least-square means differences will be calculated with 99% confidence.

Average Wear Time (AWT)

AWT (in hours) will be analyzed using a linear mixed model to test for difference between the Test and the Control groups. Lens Group, Time (1-, 2-, 4-, 8- and 12-week) and the interaction term the lens group by time will be included as fixed effects in the model; and site as random effect.

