5.2. Efficacy Endpoint(s)

5.2.1. Definition

The primary efficacy endpoints are contact lens monocular distance Visual Acuity (VA) on LogMAR scale using ETDRS charts and Eyestrain caused by glare score. VA will be evaluated under high luminance and high contrast conditions at 4 meters from ETDRS charts. Eyestrain caused by glare will be assessed using eyestrain items and will be scored using Item Response Theory.

The primary efficacy endpoints will be evaluated at 2-, 4-, 8- and 12-week follow-up visits.

The secondary endpoint is daily Average Wearing Time in hours.

The secondary efficacy endpoint will be evaluated at 2-, 4-, 8- and 12-week follow-up evaluations.

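### The visual acuity analysis splits alpha over five visits, but the hypothesis and endpoint definition name four and the Visit 2 (week 1) steps contain no logMAR test

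*SAP*

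**What the plan says.** The analysis text uses five visits. SAP 5.2.2 (Visual Acuity) models weeks 1, 2, 4, 8 and 12, compares the lenses at each of them, and sets the level: "Adjustment for multiple comparisons across time will be performed using Bonferroni's method with alpha equal to 0.01(0.05/5". The simultaneous intervals are at 99%. Protocol 9.1 has the same model: "Lens group, time (1-, 2-, 4-, 8- and 12-week) and the lens group by time interaction will be included as fixed effects". SAP 1.1 says the SAP overrides Protocol section 9 where they differ, so SAP 5.2.2 governs.

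The hypothesis and endpoint text use four visits. SAP 1.4.1 sets the hypothesis "with respect to distance monocular LogMAR visual acuity. The assessments will be made at the 2-, 4-, 8- and 12-week follow-up visits", and Protocol 4.1.3 names the same four. SAP 5.2.1 says: "The primary efficacy endpoints will be evaluated at 2-, 4-, 8- and 12-week follow-up visits".

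The Visit 2 (week 1) steps in Protocol 4.7.1 include three acuity records:

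- Step 12, entrance acuity, names no chart: "Record the distance visual acuity with the study contact lenses (OD, OS, and OU) to the nearest letter".
- Step 13, over-refraction, records Snellen acuity.
- Step 22, exit acuity, is Snellen: "Record the distance Snellen visual acuity with the study lenses (OD, OS, and OU) to the nearest letter".

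Visit 3 has the same entrance-acuity step and, in addition, a separate step headed "LogMAR (ETDRS) Visual Acuity" with charts and light levels. Visits 4, 5 and 6 have it too. Visit 2 does not.

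Two places point towards five visits. Protocol 4.1.2 says: "Both primary and secondary endpoints will be evaluated at each follow-up visit". The schedule tables (Protocol 1.8 and 4.4.1) tick logMAR acuity in one pooled follow-up column covering Visits 2 to 8.

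**The concern.** SAP 5.2.2 disagrees with the SAP's own hypothesis and endpoint definition about how many visual acuity comparisons are planned. If the Visit 2 steps are followed as written, there is no logMAR measurement at week 1. The week-1 lens-by-time cell is then empty and its least-squares mean difference cannot be estimated.

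Only four contrasts would then be tested, at a level set for five. The hypothesis is that the lenses do not differ, so a stricter difference test is not the cautious choice: it makes a non-significant result easier to obtain.

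The practical risk is that the choice is made after the data exist. The programmer would have to drop week 1 and re-split alpha, keep 0.01 for four contrasts, or substitute Snellen acuity at week 1.

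**Working it through.** **Inputs.** Overall two-sided alpha 0.05 (SAP 5.1.1); five time levels, 0.01 and 99% (SAP 5.2.2); four visits in the hypothesis and endpoint definition (SAP 1.4.1 and 5.2.1, Protocol 4.1.3); 50 completers per arm (SAP 1.5).

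**The plan's own figure.** Bonferroni level = alpha/k, interval level = 1 − alpha/k. With k = 5: 0.05/5 = 0.01 and 99%. The arithmetic is right for five comparisons.

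**With the four named visits.** k = 4: 0.05/4 = 0.0125 and 98.75%.

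**Consequences that need no assumed correlation or effect size**

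| | Level 0.01 | Level 0.0125 |
|---|---|---|
| Critical z | 2.576 | 2.498 |
| Critical t, 98 df | 2.627 | 2.545 |
| Family-wise bound, four tests | 4 × 0.01 = 0.04 | 4 × 0.0125 = 0.05 |

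Width ratio: 2.5758/2.4977 = 1.031 (z) and 2.6269/2.5446 = 1.032 (t). The 99% intervals are 3.1% to 3.2% wider than the 98.75% intervals.

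**Consequences under assumed correlations.** The documents give no usable values, so ranges are shown.

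- *Family-wise error, four tests.* One million four-variate normal draws, exchangeable visit correlation 0.3 to 0.9: 3.8% down to 2.1% at level 0.01, against 4.7% down to 2.6% at 0.0125.
- *Power at one visit.* Power = Φ(nc − z) + Φ(−nc − z), with nc = √[0.5 × 50 × 2 × d² / (1 + r)], two eyes, d in SD units and r the between-eye correlation. For d = 0.5 and r = 0.3, nc = √(12.5/1.3) = 3.10, giving 70.0% at 0.01 and 72.7% at 0.0125. For r = 0.9, nc = √(12.5/1.9) = 2.56, giving 49.6% and 52.7%. The loss is 2.7 to 3.1 points.
- *Chance of no rejection at any of the four visits when a difference exists.* Using 0.01 in place of 0.0125 raises it by 0.8 to 3.0 points at d = 0.5 and by 2.1 to 3.8 points at d = 0.25. For example, with r = 0.5 and visit correlation 0.6, it is 14.0% against 12.1% at d = 0.5, and 70.6% against 67.6% at d = 0.25.

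**Which reading the documents favour.** The version 6.0 entry in Protocol 1.7 moved both primary efficacy hypotheses and the secondary one to four visits, which agrees with the current 4.1.3. For wear time, Protocol 9.1 uses five visits and 0.01, whereas SAP 5.2.2 uses four and 0.0125. Eyestrain in the SAP also uses four and 0.0125. Wear time and the glare questionnaire are both collected at Visit 2 (steps 2 and 6), so week 1 was left out even where data exist. Among the efficacy endpoints, only visual acuity kept five, and it is the one without a Visit 2 measurement step.

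**The case against.** Within SAP 5.2.2 the numbers are coherent: five time levels, a comparison at each, and a division by five. The SAP also keeps five visits and 99% adjusted intervals for slit lamp findings and symptoms, so five is not foreign to the plan. The schedules tick logMAR at follow-up and show Snellen only at baseline and exit. On the schedule alone, logMAR is therefore the only acuity measure at Visit 2, and an ETDRS step may have been left out of the Visit 2 list by accident. Protocol 4.1.2 reads the same way. The consequence is also slight: four tests at 0.01 respect the 5% level, unadjusted 95% results are reported as well, and every hypothesis is declared exploratory.

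Much of this stands. The impact is low, and an omitted Visit 2 step cannot be ruled out. But the pooled tick also covers Visits 7 and 8, which have no logMAR step in 4.7.1, so it is weak evidence for a week-1 measurement. If week 1 was intended, then the hypothesis, the endpoint definition and the Visit 2 steps are wrong instead. Either way some text has to change.

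It is also true that a non-significant difference test is poor support for a claim of no difference, and that moving from 0.01 to 0.0125 does not cure this. That is a separate and larger point.

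**Conclusion.** The concern holds. The governing text for a co-primary endpoint plans a comparison for which the detailed procedures collect no logMAR data, and it sets an adjusted level for five comparisons where the hypothesis and endpoint definition name four.

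The effect is small: intervals about 3% too wide, a family-wise bound of 0.04 instead of 0.05, and no inflation of type I error. These figures rest only on the count of four visits. The power and non-rejection figures also depend on the assumed eye and visit correlations and effect sizes, and serve only to show that the effect is a few percentage points at most over those ranges. That the passages conflict is certain. That four visits is the intended number is the better-supported reading, but not proven. This should be corrected; it does not threaten the study.

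**What to change.** First settle whether week 1 belongs in the visual acuity analysis.

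- **If it does not (the better-supported reading):** in SAP 5.2.2 set the visual acuity time levels to weeks 2, 4, 8 and 12, alpha to 0.0125 (0.05/4) and the simultaneous intervals to 98.75%. Make the same edit in Protocol 9.1 for consistency, although the SAP overrides it. Bring the general sentence in Protocol 4.1.2 and the logMAR row of both schedule tables into line with the visit steps.
- **If it does:** keep 0.01 and 99%, add an ETDRS step to Visit 2 in Protocol 4.7.1, and add week 1 to the visual acuity hypothesis (SAP 1.4.1, Protocol 4.1.3) and endpoint definition (SAP 5.2.1).

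The first route costs wording only, with no new data, visits or subjects. The second adds one acuity test at an existing visit. Either should be done before database lock.
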